4 STUDY PLAN

4.1 Study Design

This is a prospective, open-label, investigator-initiated, convenience-enrollment, randomized-controlled trial comparing the efficacy of the ultrasound-guided three-point GNB versus conventional analgesia of atraumatic knee pain. Patients who present to the ED with atraumatic knee pain will receive plain film radiography of the knee to evaluate for acute fracture or large knee joint effusion. Patients without radiographic evidence of fracture or large knee joint effusion will be eligible for enrollment. Patients for whom there are concerns for infection, including cellulitis or septic arthritis will be excluded. Other exclusion criteria are listed in Section 5.2. We hypothesize that patients who receive a GNB will experience a greater reduction in pain and longer acting analgesia compared to those managed with conventional analgesia.

Patients who present to one of the four primary ED sites within the Penn Medicine health system (HUP, PPMC, PAH, HUP Cedar) will be eligible for inclusion as participants. Research assistants (RAs), who are present in the ED at HUP and PPMC daily, will assist with recruitment at those sites, and potentially eligible patients at PAH and HUP Cedar will be recruited by participating physicians. The study team will review inclusion and exclusion criteria with the RAs prior to the initiation of patient enrollment. Furthermore, an EPIC Haiku notification will be created to alert the study team of any patient who presents to the ED with knee pain. Prior to recruitment, it is assumed that most patients who will become participants will have been offered conventional oral, intravenous, or topical analgesics as part of their normal treatment regimen. If completion and radiologist read of plain film imaging (1) does not show evidence of acute fracture and (2) does not show evidence of a large knee joint effusion, patients will be screened for eligibility by either an RA or the performing physician. Patients with small or moderate sized effusions will be eligible for inclusion if there is no clinical concern for septic arthritis of the knee. Large effusions will be excluded as this may distort the anatomical and sonographic landmarks for performing the GNB. The physician who performs the GNB for participants may not necessarily be the physician who is primarily caring for the patient clinically in the ED.

Those patients who satisfy all inclusion criteria will be offered enrollment and consented by a participating emergency physician or RA. Upon consenting, patients will be asked to rate their knee pain on the NRS. This initial evaluation is based on the current severity of the pain, regardless of whether patients received any analgesics prior to obtaining radiography. Study will not begin until plain film imaging has been reviewed by a radiologist, at which point patients will be considered for eligibility.

Utilizing a random number generator, patients will be randomized to either the intervention arm (GNB) or the control (conventional analgesia) arm. Within the intervention arm, a three-point GNB will be performed under ultrasound guidance using 80% of ideal body weight (80% of *actual* body weight if BMI is less than 25 kg/m^2) dosing of 0.5% bupivacaine with 4 mg dexamethasone, divided into three separate aliquots (5 mL of 0.5% bupivacaine with 1-2 mg dexamethasone) which will be administered to the SMGN, SLGN, and IMGN. The performing

physician will first identify all landmarks via ultrasound, which include the superomedial and -lateral knee (aligning the probe longitudinally with the femoral condyle) and the inferomedial knee (aligning the probe longitudinally with the tibial condyle). Color doppler will be applied to note any vascular structures within the field of view of injection. The patient will be placed on the cardiopulmonary monitor prior to the GNB. The GNB will be performed via ultrasound guidance in real-time.

The control arm will be treated with oral, intravenous, or topical analgesics, as per the treating clinician's discretion. Patients will be observed on continuous cardiorespiratory monitoring in the ED for at least 30-minutes following treatment to evaluate for treatment effect and adverse events. Patients will be discharged from the ED when their pain is sufficiently controlled, and they are agreeable for discharge. Of note, patients in both treatment arms will be eligible for additional analgesics, as needed, at any point after enrollment. This will be recorded and evaluated during analysis. At either 1-hour after enrollment or at the time of discharge from the ED (whichever occurs first), patients of both treatment arms will be again asked to rate their pain severity on the NRS and asked to complete the modified APS-POQ-RED. This survey will be conducted either by RAs (during daytime hours, if available) or the performing physician (if overnight). Patients will subsequently receive a phone call approximately 24 to 36 hours after the treatment by a member of the study team (performing physician, RA, or the clinical research coordinator (CRC) from the Emergency Ultrasound Division) to evaluate the duration of analgesia. If the block is performed during overnight hours, the follow-up call will take place the next day (between 24 to 36 hours after treatment). After this assessment, the participant's involvement in the study will be concluded. Only in cases where an adverse event occurred that either requires hospitalization or ambulatory follow-up will a participant's participation last longer than 24 hours. All data collected by the RA, the CRC, or the performing physician will be stored in REDCap. The RAs will transmit all research data, including an encrypted medical record number (MRN) and all pain scale responses obtained from the study participants to the Ultrasound Division's CRC, who will be responsible for storing and managing data on REDCap.

Patients with large knee effusions will not be included in the study as large effusions can make the GNB more difficult to perform by distorting the anatomical and sonographic landmarks, and we wish to avoid the additional risk of inadvertent intra-articular injections. In our experience, we have been able to perform the GNB on patients with small and moderate sized effusions without difficulty.

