1 STUDY SUMMARY

1.1 Synopsis

Title: Ultrasound-Guided Genicular Nerve Block for Knee Pain in the Emergency Department: A Randomized Controlled Trial

Short Title: Genicular Block for Knee Pain: An RCT

Study Description: Patients who present to the emergency department (ED) at any of the clinical sites of the University of Pennsylvania Health System with atraumatic knee pain will be considered for enrollment to be randomized to receive an ultrasound-guided genicular nerve block (GNB) or conventional analgesia. Patients randomized to the intervention arm will receive a three-point GNB with weight-based dosing 0.5% bupivacaine augmented with 4 mg dexamethasone, divided into three separate aliquots to be injected around the superomedial genicular nerve (SMGN), superolateral genicular nerve (SLGN), and inferomedial genicular nerve (IMGN). This will be an open-labeled, investigator-initiated study with convenience enrollment.

Objectives: Primary Objective:

- To determine whether patients receiving a GNB for knee pain experience greater pain reduction compared to conventional analgesia

Secondary Objectives:

- To determine whether patients who receive a GNB experience a longer duration of analgesia compared to those who receive conventional analgesia
- To determine whether patients who receive a GNB report higher patient satisfaction compared to those who receive conventional analgesia
- To determine whether patients who receive a GNB have shorter ED length of stay (LOS) compared to those who receive conventional analgesia

Primary Endpoint:

- Difference in pain level as measured by NRS at pre-intervention (GNB or conventional analgesia) and at either 1-hour post-enrollment or time of ED discharge, whichever occurs first

Secondary Endpoints:	
• Difference in duration of analgesia, assessed at 24-36 hours post intervention.• Difference in APS-POQ-RED between treatment arms, assessed at either 1-hour post-enrollment or time of ED discharge, whichever occurs first.• Difference in ED LOS between treatment arms, as determined by time from enrollment in study to time of ED discharge.

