5 STUDY POPULATION

5.1 Inclusion Criteria

To be eligible to participate in this study, an individual must meet all the following criteria:

1. Patient presenting to ED with atraumatic knee pain
2. Provision of signed and dated informed consent form and stated willingness to comply with all study procedures and availability for the duration of the study
3. Equal to or over the age of 18 years
4. Have plain film radiography of the knee obtained during the encounter
5. Pain measured on NRS between 5 and 10

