7 STUDY INTERVENTION DISCONTINUATION AND PARTICIPANT DISCONTINUATION/WITHDRAWAL

7.1 Discontinuation of Study Intervention

The intervention in this study is a one-time three-point GNB performed with bupivacaine and dexamethasone. Moreover, both prior to and after the intervention, patients will continue to receive analgesia as needed in accordance with standard of care (e.g., a patient receives a GNB but still has significant pain 60-minutes afterward will be offered additional conventional analgesics, at the discretion of the primary physician).

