12 APPENDIX

12.1 Schedule of Activities (SoA)

12.2 The American Pain Societies – Patient Outcome Questionnaire Revised for the Emergency Department (APS-POQ-RED)

The following question is about the pain you experienced during your stay in the emergency department:

- On this scale, please tick the current pain you have after treatment in the emergency department (from “0” = no pain to “10” = worst possible pain).

Tick the one number below that describes how your current pain interferes with or prevents you from different activities (from “0” = no did not interfere to “10” = completely interfered).

- During activities in bed such as turning, sitting up, repositioning:
- During activities out of bed such as walking, sitting in a chair, standing:

On this scale, please tick the number describes how your current pain causes you to feel different emotions (from “0” = not at all to “10” = extremely)

- Anxious
- Frightened
- Helpless

In the emergency department, how much pain relief did you receive?

- Please tick the percentage that best shows how much relief you have received for all your pain treatments combined.

This question asks about your overall satisfaction with your pain control.

- Tick the number that best shows how satisfied with the results of your pain treatment in the emergency department (from “0” = extremely dissatisfied to “10” = extremely satisfied)

Modified from:

END OF DOCUMENT

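### The objectives state an unqualified contrast of GNB versus conventional analgesia, but the design compares GNB with further conventional analgesia in patients still at NRS 5-10, many of them after initial analgesia

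*Protocol*

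**What the plan says.** The primary objective in Protocol 1.1, repeated in section 3, is "To determine whether patients receiving a GNB for knee pain experience greater pain reduction compared to conventional analgesia". The hypotheses in 9.1 set mean pre/post change under GNB against mean pre/post change under conventional therapy. Neither mentions earlier or concurrent analgesia.

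Other sections describe the setting in which that contrast is made:

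- **Before recruitment (4.1):** "it is assumed that most patients who will become participants will have been offered conventional oral, intravenous, or topical analgesics".
- **Entry (5.1):** "Pain measured on NRS between 5 and 10".
- **Baseline score (4.1):** "This initial evaluation is based on the current severity of the pain, regardless of whether patients received any analgesics prior to obtaining radiography". No minimum interval since an earlier dose is set.
- **Control treatment (4.1):** "The control arm will be treated with oral, intravenous, or topical analgesics, as per the treating clinician's discretion". These are the same routes of treatment assumed to have been offered already.
- **After enrollment (4.1):** "patients in both treatment arms will be eligible for additional analgesics, as needed, at any point after enrollment". Section 7.1 adds that "both prior to and after the intervention, patients will continue to receive analgesia as needed in accordance with standard of care".

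Section 6.4 has medications given before the study starts, and any given afterwards, documented in the medical record and in REDCap. Section 4.1 promises that additional analgesic use will be looked at in the analysis. The primary model in 9.4.1 has two factors, treatment arm and time.

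**The concern.** The objective reads as a comparison of two alternative treatments for knee pain in the ED. A patient whose pain falls below NRS 5 after the first conventional analgesic cannot enter. The conventional treatment is therefore tested partly in people whose pain has persisted despite it, and controls then receive more treatment of the same kind. That is a sensible pragmatic question, but it is narrower than the one written in the objectives.

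What is at stake is mainly the conclusion. A positive result reported in the words of the objective would be read as applying to first-line treatment of all such patients, including those who would have responded to a first conventional dose. The trial has no information on them.

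A second, smaller matter is precision. A drug given shortly before baseline may still be taking effect in the hour before the primary score, so prior dosing may predict change in NRS. It is recorded but has no place in the stated primary model.

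**Working it through.** The main point rests on no figure in the plan, so it is settled by setting the sections side by side.

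**Step 1. Who is randomised.** Sections 4.1 and 5.1 together give patients with NRS 5-10 at consent, most of them assumed to have been offered conventional analgesics beforehand. No percentage is given.

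**Step 2. What each arm is assigned.** Under 4.1 and 6.1.1 the intervention arm is assigned GNB and the control arm is assigned conventional analgesics. Only controls are assigned conventional drugs.

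**Step 3. What both arms may also get.** Sections 4.1 and 7.1 allow as-needed analgesia, at any point after enrollment. This includes the interval before the primary NRS, which is taken at 1 hour or at discharge, whichever comes first.

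**Step 4. The resulting contrast.** GNB versus further conventional analgesia as the next treatment, with as-needed analgesia in both arms, in patients with NRS 5-10 at randomisation. Sections 1.1, 3 and 9.1 omit the population and background parts of this.

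**Step 5. Is prior dosing a bias?** No. It precedes randomisation, so its expected effect is equal in the two arms and cancels in the difference. Only chance imbalance remains. Its possible size can be shown only with assumed inputs, so the following is illustrative.

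- From 9.2: 17 per arm, target difference 1.6, SD 2.0.
- Assumed, not in the documents: a pre-treated share p of 0.6 to 0.8, and a fall b of 1 to 2 points after baseline attributable to a recent dose.
- With two independent Binomial(17, p) counts, the probability that the arms differ by at least 4 pre-treated patients is 0.220 (p = 0.6), 0.189 (p = 0.7) and 0.130 (p = 0.8).
- Shift from a 4-patient imbalance = (4/17) × b = 0.24 (b = 1) to 0.47 (b = 2), or 15% to 29% of 1.6.
- Standard error of the arm difference = 2.0 × √(2/17) = 0.69. The shift is thus about 0.3 to 0.7 of a standard error, which is ordinary sampling variation that the confidence interval already covers.

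**Step 6. What a covariate could gain.** If prior dosing adds b points in a share p, it accounts for b²p(1−p) of the variance of change, which is 2.0² = 4.0 in the plan.

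- b = 1: 0.16 to 0.24, or 4% to 6% of 4.0.
- b = 2: 0.64 to 0.96, or 16% to 24% of 4.0.
- If it predicts nothing, the gain is nil. The cost is one residual degree of freedom, 34 − 2 = 32 falling to 34 − 3 = 31.

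**The case against.** The strongest reply is that the protocol hides nothing. Sections 2.2 and 4.2 present the target as breakthrough knee pain, and 4.2 says that standard treatments often fail in it. Sections 4.1 and 7.1 state the earlier and later analgesia openly. After randomisation the arms do differ as GNB versus conventional treatment, so the stated contrast is incomplete rather than false. This stands, and it makes the point one of imprecise wording and not of a concealed or invalid comparison.

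A second reply is that covariates and the handling of additional analgesia are commonly left to the SAP. This stands in part. The missing covariate is not in itself an error, and scoring pain regardless of as-needed drugs is a legitimate pragmatic choice. The objectives and hypotheses, however, are protocol content. Since 9.4.1 already writes out the primary model, it is a natural place to name one covariate.

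A reader might infer three stronger things that the protocol does not support:

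- **That this is an add-on trial.** The GNB arm is not assigned conventional drugs; it may receive them if needed. The example in 7.1 is a patient still in pain 60 minutes after the block, around or after the time of the primary score. Section 9.4.2 also counts GNB as the initial treatment from which time to additional analgesia runs.
- **That the stated contrast holds for only a small share of patients.** Taking the protocol's assumption to mean 60-80% pre-treated would leave 20-40%, but no share is given, and offered is not received.
- **That prior analgesia biases the estimate.** It precedes randomisation and can be unbalanced only by chance.

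**Conclusion.** The point holds as a matter of scope. The randomised comparison is sound for GNB versus further conventional analgesia as the next treatment in patients at NRS 5-10, with as-needed analgesia in both arms. The objectives, hypotheses and any conclusion written in their words claim more than that.

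No numerical size can be derived from the protocol. How far the enrolled patients differ from all ED patients with knee pain depends on how many actually received analgesia first, which is not stated. The 0.24 to 0.47 point shift and the 4% to 24% variance shares are illustrations on assumed inputs and should not be quoted as findings. The covariate is a low-cost improvement whose value depends on how prognostic prior dosing proves to be.

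Some background overlap also reaches a secondary measure. The relief item in Appendix 12.2 reads "Please tick the percentage that best shows how much relief you have received for all your pain treatments combined", so it can credit doses given before randomisation in either arm. This supports stating the background explicitly but does not change the conclusion.

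**What to change.** 1. **Restate the contrast** in 1.1, 3 and 9.1 along these lines: GNB versus further conventional analgesia as the next ED treatment, with as-needed analgesia permitted in both arms, in patients with NRS 5-10 at randomisation, whether or not they have already received analgesia. Limit the conclusion to those terms, and do not call the comparison add-on. Cost: a wording change and a narrower claim.

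2. **Prespecify one covariate** for the arm comparison of change in 9.4.1: analgesic received before the baseline NRS, yes or no, from the data that 6.4 already collects. It should be the drug received, not offered. In the arm-by-time model it must enter with its interaction with time, or equivalently as a covariate in a linear model of change on arm. As a main effect alone it would not adjust the comparison of change. Cost: one degree of freedom, and no new data.

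3. **Do not adjust for analgesia given after randomisation** in the same way, because the assigned arm can influence it.

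4. **Optional:** record an NRS just before any additional analgesic given ahead of the primary score, for a sensitivity analysis. This would give the promise in 4.1 a usable measurement, at the cost of one extra question in some patients. The main point does not depend on it.

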2.2.4 Dosing Rationale

The weight-based maximal safe dosing for bupivacaine is 2.5 mg/kg. To minimize the risk of LAST, we will utilize weight-based dosing at 80% of the maximal safe dosing which will allow for effective and prolonged analgesia while minimizing the risk of complications and LAST. Patients with body mass index (BMI) greater than 25 kg/m² will receive a total of 80% of their ideal body weight dosing in bupivacaine. Patients with a BMI of equal to or less than 25 kg/m² will receive a total of 80% of their actual body weight dosing in bupivacaine. This total dose will

be divided into three equal aliquots that will be injected around each of the three targeted genicular nerves. The use of dilute bupivacaine (0.5%) will allow for better spread to target nerves as well as a slower injection rate of anesthetic which is safer for monitoring for symptoms of LAST.

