4.3 Justification for Dose

For the GNB arm, the maximum recommended dosing for bupivacaine for regional anesthesia is 2.5 mg/kg. To minimize the risk of LAST, we will utilize weight-based dosing at 80% of the maximal safe dosing which will allow for effective and prolonged analgesia while minimizing the risk of complications and LAST. Patients with body mass index (BMI) greater than 25 kg/m^2 will receive a total of 80% of their ideal body weight dosing in bupivacaine. Patients with a BMI of equal to or less than 25 kg/m^2 will receive a total of 80% of their actual body weight dosing in bupivacaine. This total amount will be divided into three equal aliquots that will be injected around the three genicular nerves), which will be well below the recommended maximal dose for both female and male patients. Dexamethasone dosing ranging from 4-8 mg has shown to prolong regional anesthesia by the prevention of enzymatic processing of local anesthetics, and is commonly used as an adjuvant in both the perioperative setting and in the ED. Given the relatively low volume and dose of anesthetic that will be administered, we plan to supplement the blocks with 4 mg dexamethasone, divided equally into the three injections.

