6 STUDY INTERVENTION

6.1 Study Intervention(s) Administration

6.1.1 *Study Intervention Description*

The study interventions are either conventional analgesia or a one-time three-point GNB with weight-based 0.5% bupivacaine and 4 mL dexamethasone divided into three separate injections, ~~around the SMGN, SLGN, and IMGN. Bupivacaine and dexamethasone are commercially~~ available and are being used in accordance with approved labeling.

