6.2.2 Formulation, Appearance, Packaging, and Labeling

For the GNB arm, bupivacaine 0.5% is stored in either the Omnicell (immediately available medication storage within the emergency department) or central pharmacy, where it can be sent down to the ED. The medication is stored at room temperature in individually sealed vials. No preparation other than drawing up the medication with a needle and syringe will be necessary, which will be the responsibility of the participating physician administrating the GNB. Vials are single use and clearly labelled. Bupivacaine will be mixed at the bedside with dexamethasone prior to injection. Bupivacaine on formulary is manufactured by Xellia Pharmaceuticals LLC. Dexamethasone 4mg/mL is also available in the ED Omnicell and commonly utilized in emergency patient care. Bupivacaine 0.5% is distributed by Hospira and dexamethasone sodium phosphate 4mg/mL is distributed by Hikma.

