6.2.4 Preparation

For the GNB arm, bupivacaine 0.5% is available in single-use vials as a ready-to-use liquid. It will be drawn up with a blunt needle and syringe and requires no special preparation prior to administration. In this case, three separate syringes will be loaded with the appropriate volume 0.5% bupivacaine (weight-based dosing as described above). To each syringe, 1-2 mg of dexamethasone will be added to the bupivacaine (for a total of 4 mg of dexamethasone).

Preparation of medications for the control arm will be prepared and administered to the patient by nursing as per the electronic orders, as is standard of care.

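### Section 4.1 fixes each bupivacaine aliquot at 5 mL, which fits the protocol's weight-based dose only at 37.5 kg, and section 6.1.1 gives dexamethasone as 4 mL where every other section says 4 mg

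*Protocol*

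**What the plan says.** **Bupivacaine.** Protocol sections 2.2.4 and 4.3 give a maximum of 2.5 mg/kg, and section 4.3 says "we will utilize weight-based dosing at 80% of the maximal safe dosing". Both sections split that total into three equal parts. Section 6.1.2 (dosing) repeats the weight rule. Section 6.2.4 (preparation) also follows it: "three separate syringes will be loaded with the appropriate volume 0.5% bupivacaine (weight-based dosing as described above". Section 4.1 states the weight rule too, but the same sentence then has the dose "divided into three separate aliquots (5 mL of 0.5% bupivacaine with 1-2 mg dexamethasone".

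**Dexamethasone.** Section 4.3 plans "4 mg dexamethasone, divided equally into the three injections". The total is also 4 mg in sections 1.1, 4.1, 6.1.2, 6.2.4 and 6.5. Section 6.1.1, which describes the intervention, instead has "weight-based 0.5% bupivacaine and 4 mL dexamethasone divided into three separate injections". The stock strength is in section 6.2.2: "Dexamethasone 4mg/mL is also available in the ED Omnicell".

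**Which body weight.** Section 2.2.4 reads "Patients with a BMI of equal to or less than 25" for dosing on actual weight, and section 4.3 agrees. Section 2.3.1 puts a BMI of exactly 25 kg/m² on ideal weight. Sections 2.3.3, 4.1 and 6.1.2 likewise keep actual weight for BMI below 25.

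**The concern.** A weight-based total and a fixed aliquot volume can both be right at only one body weight. If that weight lies outside the usual adult range, section 4.1 contradicts itself and also contradicts the dosing and preparation sections. A volume of dexamethasone in place of a mass is a second conflict, because it can be drawn up literally from a 4 mg/mL vial.

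What is at stake is the definition of the treatment under test. Under sections 6.2.1, 6.2.2 and 6.2.4 the performing physician receives unopened vials, draws up the drugs and mixes them at the bedside, so the injected amount depends on how that physician resolves the conflict. Blocks may be given in four emergency departments, and the planned block arm has 17 patients, so each patient dosed on a different reading is 1/17 = 5.9% of the arm. A smaller bupivacaine dose could weaken the block and so bear on the primary pain endpoint. Dexamethasone is added to prolong the block, and duration of analgesia is a secondary endpoint.

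**Working it through.** **Inputs from the protocol**
- Maximum bupivacaine dose: 2.5 mg/kg (2.2.4, 4.3, 6.1.2)
- Fraction used: 80% (2.2.4, 4.3)
- Concentration: 0.5%, which is 5 mg/mL
- Injections: three, in equal parts (2.2.4, 4.3)
- Fixed aliquot: 5 mL (4.1)
- Dexamethasone: 4 mL (6.1.1) or 4 mg (elsewhere); stock 4 mg/mL (6.2.2); cited range 4 to 8 mg (4.3)

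**Step 1. Dose under the weight rule.** 0.80 × 2.5 = 2.0 mg/kg. In volume, 2.0 / 5 = 0.4 mL/kg in total, or 0.4 / 3 = 0.133 mL/kg per site.

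**Step 2. Dose under the fixed aliquot.** 3 × 5 mL × 5 mg/mL = 75 mg (15 mL) at any weight.

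**Step 3. Where the two agree.** 75 / 2.0 = 37.5 kg. Two other readings do not reconcile them:
- Using the full 2.5 mg/kg, they agree at 75 / 2.5 = 30 kg.
- Taking 5 mL as the total volume (25 mg), they agree at 25 / 2.0 = 12.5 kg. The 1-2 mg of dexamethasone beside it fits a per-aliquot reading anyway: 3 to 6 mg over three aliquots brackets the 4 mg total.

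**Step 4. Size of the gap.** The protocol gives no weights, so these dosing weights are assumed.

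| Dosing weight | Weight rule, total | Per site | Fixed dose, total | Fixed / rule | Rule / fixed | Fixed, mg/kg | Fixed as share of 2.5 mg/kg |
|---|---|---|---|---|---|---|---|
| 50 kg | 100 mg (20 mL) | 6.7 mL | 75 mg | 75% | 1.3 | 1.50 | 60% |
| 60 kg | 120 mg (24 mL) | 8.0 mL | 75 mg | 63% | 1.6 | 1.25 | 50% |
| 70 kg | 140 mg (28 mL) | 9.3 mL | 75 mg | 54% | 1.9 | 1.07 | 43% |
| 80 kg | 160 mg (32 mL) | 10.7 mL | 75 mg | 47% | 2.1 | 0.94 | 37.5% |

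The planned share of the maximum is 80% throughout. The fixed dose would reach the 2.5 mg/kg limit only at 30 kg.

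**Step 5. Dexamethasone.** 4 mL × 4 mg/mL = 16 mg. Against the intended total, 16 / 4 = 4 times. Section 4.3 states "Dexamethasone dosing ranging from 4-8 mg has shown to prolong regional anesthesia", and 16 / 8 = 2 times the top of that range. The intended 4 mg is 4 / 4 = 1 mL of stock.

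**Step 6. BMI of exactly 25.** Sections 2.2.4 and 4.3 put it on actual weight. Section 2.3.1 puts it on ideal weight, and sections 2.3.3, 4.1 and 6.1.2 keep actual weight for BMI below 25. The conflict exists only at that one value.

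**The case against.** The strongest reply is that no careful reader would be misled. Section 4.1 gives the weight rule before the 5 mL, which is only in parentheses. The sections that govern dosing and syringe loading (6.1.2 and 6.2.4) are consistently weight-based, and staff are to be trained on the protocol. The 4 mL appears once against 4 mg in six other sections, and pharmacists approve the orders (6.2.1). The drugs given are recorded (6.4), so the delivered dose can be recovered.

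Much of this is fair. The dexamethasone figure is very probably a unit slip, the BMI point is minor, and someone reading section 4.1 meets a conflict, not a plain instruction to under-dose. The upper end of the range also needs care. Actual weight is used only up to a BMI of about 25, so an actual dosing weight of 80 kg implies a height of at least √(80/25) = 1.79 m. At 45 kg the rule gives 90 mg, and the ratio falls to 90 / 75 = 1.2.

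The contradiction remains. Nor is it certain that 5 mL is the mistake. Section 2.2 describes the classical block as using a small volume, and section 4.3 justifies dexamethasone partly by the low volume and dose of anaesthetic. Both sit more easily with 15 mL in total than with 20 to 32 mL at 80% of the maximum. Recording the dose makes it recoverable but does not make it uniform.

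**Conclusion.** The point holds and should be fixed. As written, the block has two bupivacaine doses that coincide only at a dosing weight of 37.5 kg. For assumed weights of 50 to 80 kg the weight rule gives 1.3 to 2.1 times the fixed dose. The contradiction itself follows from the protocol's own figures; only the size of the gap rests on the assumed weights.

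The 5 mL reading errs toward under-dosing, so this is not a toxicity finding for realistic adults. The 4 mL of dexamethasone, taken literally, is a fourfold dose, though it is most likely a slip. Neither issue affects the validity of the randomised comparison or its type I error. What suffers is the reproducibility of the intervention being tested.

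**What to change.** 1. **Bupivacaine.** Ask the sponsor which dose is intended.
   - *Weight-based, as most sections say:* in section 4.1 replace the 5 mL with one third of the weight-based volume, that is 0.4 mL per kg of dosing weight divided by three.
   - *5 mL per site:* state 15 mL (75 mg) as the dose throughout and remove the weight rule.
2. **Dexamethasone.** In section 6.1.1 write 4 mg in total (1 mL of the 4 mg/mL stock).
3. **BMI boundary**, if weight-based dosing stays. In sections 2.2.4 and 4.3 use actual weight for BMI below 25 kg/m² and ideal weight for 25 or above, to agree with 2.3.1, 2.3.3, 4.1 and 6.1.2.

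**Cost.** The weight-based route changes wording in four sections (2.2.4, 4.1, 4.3 and 6.1.1). The fixed-dose route also needs edits wherever weight dosing is described, including 1.1, 2.3.1, 2.3.3, 6.1.2 and 6.2.4. Either way, check that the order instructions match. No patients, procedures or data items are added.
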